Dose Higher-doses of botulinum toxin show better intensity and duration in the treatment of Gummy Smile?

This study is registered at clinicaltrials.gov (NCT05127018).

Document Date: November 20, 2019

Study Protocol :

The smile is one of the universal facial expressions of humans. Gingival smile is characterized by gingival exposure of >3 mm upon smiling. The degree of gingival exposure can vary substantially between patients, with patients presenting gingival exposure of up to more than 10 mm. The prevalence of gingival smile is 10.57%, and it is more frequently observed in females. Although gingival smile is merely an anatomical variation, it can be considered unattractive, causing significant distress and impacting one's quality of life. Moreover, most orthodontists and dentists regard gingival smile as an important risk factor for dental treatment.

Gingival smile involves a complex interaction between the facial muscles, bone, and skin; specifically, it is related to hypermobility of the upper lip with muscle involvement and alterations in anatomical features, such as a short clinical dental crown, anterior dentoalveolar extrusion, maxillary excess, and a short upper lip. Therapies for gingival smile range from botulinum toxin injections to surgical interventions according to its etiology. Although the outcomes of surgical procedures are long-lasting, botulinum toxin type A treatment is an easy and fast outpatient procedure that requires no downtime and has high efficacy rates. Nevertheless, there are controversies around the optimal dose and injection site of botulinum toxin type A. Moreover, the efficiency of botulinum toxin type A for gingival smile varies markedly between studies, with the improvement rate of gingival exposure ranging from 62.06% to 98%. Sucupira and Abramovitz advocate the use of a low amount of botulinum toxin type A of 1.95 U per side for the treatment of gingival smile. They noted an average satisfaction level of 9.75 on a 10-point scale with this approach. They claimed that higher doses did not provide further benefit, and, in fact, could lead to lip ptosis, asymmetry, and

excessive upper lip length. However, Polo disagreed with their argument, claiming 2-5 U injection of botulinum toxin type A according to the severity of gingival smile. In this regard, Garcia and Fulton showed that low-dose injection of botulinum toxin per muscle (2-5 IU) was as effective as higher doses. Though prior studies have demonstrated a correlation between higher doses of botulinum toxin and intensity and duration of muscle paralyses, no conclusion can be drawn regarding duration and intensity of doses used in the recent studies. A safe approach advocated by some authors consists of starting with low toxin doses initially, with retouching at a later stage if required. In this study, the investigators compared botulinum toxin type A efficiency using the average-dose method (2-5 U botulinum toxin type A per side determined according to the severity of anterior gingival smile) and, the higher-dose method (3-10 U botulinum toxin type A per side determined according to the severity of anterior gingival smile). The investigators aimed to assess the efficiency and duration of these approaches, as well as side effects and patients' satisfaction with treatment. In this prospective self-controlled study, healthy participants with gummy smile underwent two treatment methods.

The inclusion criteria to be considered for the study were as follows: 1) healthy participants with anterior gingival exposure of ≥ 3.0 mm during unrestricted, "full-blown" smiling; 2) participants between 18 and 60 years old. The following exclusion criteria were used for the study participants: 1) complications to botulinum toxin A; 2) paralysis of the face; 3) previous disease and/or treatment that affected the position of the gingiva or upper lip; 4) botulinum toxin A injection in the head or neck region within the previous year; 5) are currently receiving or have received active orthodontic treatment, including vertical dimension treatment, for extrusion or intrusion; 6) occurrence of periodontal disease; 7) refused to participate; 8) loss to follow-up.

First, participants were injected with the average-dose, which the dose was individualized according to the severity of anterior gingival exposure pretreatment. For mild gingival smile (3-5 mm), a single-site injection of 2 U botulinum toxin type A [total, 4 U] at both the right and left levator labii superioris alaeque nasi muscles) was administered. For moderate (5-7 mm) and severe (≥ 7 mm) gingival smile, 3 U and 5 U of botulinum toxin type A, respectively,

were injected per side (total, 6 U and 10U, respectively). The injection points were located at bilateral levator labii superioris alaeque nasi muscles and at the Yonsei point, with half doses administered at each point. Data were collected at baseline and at four, 12, 48, weeks follow-up.

And 8 months after the first injection, all the patients underwent second injection of the higher-dose method.

With this method, patients were administered botulinum toxin type A after 8 months when the effect of the previous injection had vanished. The injection dose (U) per side was set as the absolute value of the preoperative anterior gingival exposure (mm). For example, if the preoperative anterior gingival exposure was 5mm, then the patient would be injected with 5 U of botulinum toxin per side (total, 10U). The injection points were located at bilateral levator labii superioris alaeque nasi muscles and at the Yonsei point, with half doses administered at each point. Data were collected at baseline and at four, 12, 48, weeks follow-up.

Statistical Analysis Plan :

Data entry will be managed using WJX procedure (Ranxing Information Technology Co., Ltd., Changsha, China) and accuracy was ensured by double entry and validation. All statistical analyses were performed using SPSS software v. 20.0 (IBM Corp., Armonk, NY). The mean and standard deviation were used to describe normally distributed numerical values, and a paired-samples t-test was used to identify differences. The Wilcoxon signed-rank test was used for non-normally distributed numerical values, and the McNemar-Bowker test was used to compare dichotomous variables. A P value of <0.05 was considered statistically significant.

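### Loss to follow-up is listed as an exclusion criterion and no all-injected set is defined, so an injected participant who is later lost can be excluded together with data already collected

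*Combined protocol and SAP*

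**What the plan says.** In the Study Protocol section, the exclusion list opens with "The following exclusion criteria were used for the study participants" and closes with "7) refused to participate; 8) loss to follow-up". Most of the other items describe a person's history or condition at entry. The list does not separate conditions checked before the first injection from events after it.

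The aims are broad: "The investigators aimed to assess the efficiency and duration of these approaches, as well as side effects", and also patients' satisfaction.

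Each participant is to receive the average dose first and the higher dose later: "And 8 months after the first injection, all the patients underwent second injection of the higher-dose method". The visit schedule is given in the same words for each injection: "Data were collected at baseline and at four, 12, 48, weeks follow-up".

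The Statistical Analysis Plan section gives three methods, all of them paired. If values are normal, "a paired-samples t-test was used to identify differences". Non-normal values go to Wilcoxon's signed-rank procedure. For outcomes with two categories, "the McNemar-Bowker test was used to compare dichotomous variables". Apart from these it covers software, double data entry, descriptive statistics and the significance level. It defines no all-injected, safety or full-analysis set, no way of handling missing data, and no reporting of losses.

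**The concern.** An eligibility criterion should be decidable before treatment. Loss to follow-up is not. If it is applied to people already injected, membership of the study set depends on something that happens after treatment and may be related to its result. A participant who dislikes the outcome, or has a side effect, may be less likely to return; so may one who is content and sees no reason to come back.

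Side effects and satisfaction are stated aims, and the background reports a claim that higher doses could cause drooping, asymmetry and excessive length of the upper lip. If injected people leave both numerator and denominator, the per-dose side-effect and satisfaction figures describe only those who stayed, and a reader cannot see how many did not.

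**Working it through.** The documents give no figure to reproduce: no sample size, loss rate, event rate or standard deviation. The check is therefore of the text, then of the schedule, then an illustration on assumed inputs.

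**1. What follow-up means in this document.** Apart from criterion 8, the word appears only in the two visit schedules, where it means visits at 4, 12 and 48 weeks after an injection. Reading criterion 8 as covering injected participants is consistent with that use. Nothing in the Statistical Analysis Plan brings such participants back in.

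**2. Does criterion 8 do anything that the paired tests do not?** Taking the 8-month interval and the 48-week visits at face value:

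- 8 months = 8 × 30.4375 / 7 = 34.8 weeks.
- Average-dose visits, in weeks from the first injection: 4, 12, 48.
- Higher-dose visits: 34.8 + 4 = 38.8; 34.8 + 12 = 46.8; 34.8 + 48 = 82.8.
- Loss can therefore occur over about 83 weeks.

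Two cases:

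| Last seen | Data in hand | Paired tests alone | Criterion 8, if applied after injection |
|---|---|---|---|
| Before the second injection | First-period data only | Omit from the dose comparison | Also drops first-period data from the average-dose summary |
| 12 weeks after the second injection (week 46.8) | 4 of 6 post-injection visits; pairs complete at weeks 4 and 12 | Keep at weeks 4 and 12 | Drops both complete pairs and the data from both periods |

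So the criterion adds something to pairing. In the dose comparison, the addition is limited to visits where the pair is complete. In the per-dose summaries, it reaches all data recorded before loss.

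The average-dose week-48 visit falls 48 − 34.8 = 13.2 weeks after the second injection. The passages on the interval and on the visits need to be reconciled separately, and the figures of 83 weeks and 4 of 6 visits depend on them.

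**3. Illustration for side effects (all inputs assumed).** Let d be the proportion of injected participants lost, and p_ret and p_lost the rates in those retained and lost.

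All-injected rate = (1 − d) × p_ret + d × p_lost

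With p_ret = 10%, which is what a retained-only report would show:

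| p_lost | d = 5% | d = 10% | d = 20% |
|---|---|---|---|
| 5% | 9.75% | 9.5% | 9% |
| 10% | 10% | 10% | 10% |
| 30% | 11% | 12% | 14% |

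For example, d = 20% and p_lost = 30%: 0.80 × 0.10 + 0.20 × 0.30 = 0.14.

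**4. Illustration for satisfaction and gingival exposure (all inputs assumed).** The retained mean differs from the all-injected mean by d × D, where D is the retained-minus-lost difference. For D = 0.5 SD and d = 5%, 10%, 20%, this is 0.025, 0.05 and 0.10 SD. For D = 1 SD it is 0.05, 0.10 and 0.20 SD. For D = 0 it is 0. The sign follows the sign of D.

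**5. Bounds where side-effect status is truly unknown.** Let u be the proportion of those injected who have no post-injection side-effect assessment in that period, and p the rate in those assessed.

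Low = p × (1 − u); high = p × (1 − u) + u

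With p = 10% and u = 5%, 10%, 20%: 9.5–14.5%, 9–19%, 8–28%. The width equals u. These bounds do not apply to someone lost after an assessment, whose status up to that visit is known.

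**The case against.** Four arguments weigh against the point.

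*Recruitment losses may have been meant.* The criterion follows directly after refusal to take part, which is a recruitment event. This is plausible, but the text sets no such limit, and a one-line clarification would settle it.

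*Nobody may have been lost.* The document says "And 8 months after the first injection, all the patients underwent second injection of the higher-dose method". Taken literally, that rules out loss before month 8, though the phrase may cover only those who returned; the text does not say which. Either way, 48 weeks of visits remain after the second injection, so the statement does not close the question. It does mean that the documents show no actual loss.

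*The paired tests already drop incomplete participants.* True for anyone without second-period data, and this narrows the effect on the dose comparison. It does not cover complete pairs at weeks 4 and 12, or per-dose summaries that need no pairing.

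*The consequence can be overstated.* A reader might infer that the plan removes every lost participant and discards their data. The documents do not support that: they never say how many missed visits count as loss, nor what happens to data already recorded. What stands is that the text permits such removal and nothing prevents it.

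Gingival exposure is also not named as an endpoint in so many words. It is inferred from the stated interest in efficiency, from its use for eligibility and dosing, and from the improvement measure cited in the background.

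**Conclusion.** The point holds as a defect that should be fixed. The plan lists a post-enrolment event as an exclusion, does not confine it to the time before injection, and has no all-injected set to protect data already collected. This can bias the per-dose side-effect, satisfaction and efficiency summaries and hide attrition. In the paired dose comparison, the added effect is confined to visits with complete pairs.

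No size or direction can be derived from the documents. On the assumed inputs, the retained-only side-effect rate of 10% compares with an all-injected rate between 9% and 14%, and means shift by 0 to 0.20 SD in either direction. There is no bias if nobody is lost or if loss is unrelated to outcome.

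A reader might also infer that side effects will be understated. That does not follow: if those lost did better than those retained, the retained-only rate would be too high.

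**What to change.** 1. Delete criterion 8 from the exclusion list. Report losses in the participant flow, with numbers and reasons by period. If candidates lost before the first injection were meant, count them there.
2. For each injection, define the set of all participants injected. Report side effects with the number injected as denominator, using everything recorded up to the last visit. Show how many had no post-injection side-effect assessment in that period, and apply none-affected and all-affected bounds to those participants only.
3. Report satisfaction and gingival exposure by dose for all with data at each visit, with the numbers injected and missing.
4. Keep the paired tests for the dose comparison, using every complete pair at each visit and labelling the result as complete pairs. A mixed-model sensitivity analysis at weeks 4 and 12 is optional. Because the dose order is fixed, participants with one period would nearly always contribute average-dose data only, and the result would rest on data being missing at random.

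The cost is one criterion deleted, a short paragraph on analysis sets and missing data, and a little more reporting. No visits or participants are added, and the changes also work on data already collected. The reported figures may move in either direction.

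### As written, the average-dose week-48 reading falls about 13 weeks after the higher-dose injection; separately, the fixed order leaves dose inseparable from a second-injection effect

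*Combined protocol and SAP*

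**What the plan says.** The Study Protocol describes one group in which each person receives both methods in the same order. The opening step is "First, participants were injected with the average-dose, which the dose was individualized according to the severity of anterior gingival exposure pretreatment". At 8 months, "all the patients underwent second injection of the higher-dose method". No randomised order, concurrent control or blinding is described.

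The interval is justified by a statement that "patients were administered botulinum toxin type A after 8 months when the effect of the previous injection had vanished". No criterion for this is given, and no comparison of the two pre-injection baselines is planned.

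The same follow-up sentence stands under each method: "Data were collected at baseline and at four, 12, 48, weeks follow-up". The aims include how long the effect lasts: "The investigators aimed to assess the efficiency and duration of these approaches, as well as side effects".

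The Statistical Analysis Plan names a paired t-test, the Wilcoxon signed-rank test and the McNemar-Bowker test, with a 0.05 threshold. It does not say which visits are paired, whether the tests run within or between methods, or whether raw values or changes are analysed. No sample size or standard deviation is given.

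**The concern.** There are two separate problems.

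The first is timing. A 48-week follow-up does not fit inside an 8-month period. Taken literally, the last average-dose reading is made after the participant has had the higher dose, so it is not an average-dose reading at all. Duration appears in both the title and the aims, and week 48 is the only listed visit later than week 12. The late comparison is where the duration question would be answered.

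The second is order. With one sequence for everyone, the difference between methods is the dose effect plus anything that differs between a first and a second injection. Possible examples, none of them named in the documents, are the injector's experience, the participant's expectation, and satisfaction judged against the first result. A significant paired difference would read as a dose effect whichever of these produced it.

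**Working it through.** The plan states no figure that can be reproduced here. The check uses its calendar and its design.

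**1. Timing.** Inputs from the Study Protocol: injection 2 at 8 months; readings at weeks 4, 12 and 48 after each injection.

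- 8 months in weeks: 8 × 365.25 / 12 / 7 = 34.79.
- Average-dose week 48, counted from injection 2: 48 − 34.79 = 13.21 weeks.
- Higher-dose week-12 visit, counted from injection 1: 34.79 + 12 = 46.79. The average-dose week-48 reading comes 48 − 46.79 = 1.21 weeks after it.
- Sensitivity to the length of a month: 30 days gives 8 × 30 / 7 = 34.29 and a gap of 13.71 weeks; 31 days gives 35.43 and 12.57 weeks; 4-week months give 32 and 16 weeks. The reading falls after injection 2 in every case.
- Week 48 in months: 48 × 7 / (365.25 / 12) = 11.04. Injection 2 would have to be at about 11 months or later to leave that reading clean.

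**2. What a week-48 comparison would measure.** Let A(t) and H(t) be the mean effects of the average and higher dose t weeks after injection. The intended contrast is H(48) − A(48). If the average-dose effect has gone by 8 months, as the protocol says, the reading labelled average dose at week 48 reflects H(13.2). The contrast becomes H(48) − H(13.2), which contains no average-dose term. If the higher dose wanes between those times, the average dose appears better by the amount of waning. A within-method test of average-dose week 48 against the first baseline would be affected too, because it would pick up H(13.2). The Statistical Analysis Plan does not say whether either test is intended.

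**3. What remains.** Clean readings after both injections exist at weeks 4 and 12. The second baseline, at about week 35, is a late average-dose reading, but the higher-dose schedule has no visit between weeks 12 and 48 to match it.

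**4. Order.** Write the mean in each period as intercept + dose + period. Period 1 has (1, 0, 0) and period 2 has (1, 1, 1). The dose and period columns are identical, so the rank is 2 for 3 parameters. Adding a period term to the model cannot help, and changing the test cannot help. Adding the reverse sequence contributes rows (1, 1, 0) and (1, 0, 1) and raises the rank to 3. The cause is the single sequence.

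**5. The two baselines.** A second baseline lower than the first could be residual effect. It could also be regression to the mean, because entry requires "healthy participants with anterior gingival exposure of ≥ 3.0 mm during unrestricted" smiling; this applies if the entry reading also serves as the first baseline, which the protocol does not state. The direction of any bias from residual effect is unclear as well. The higher dose in units per side equals exposure in mm, without saying which baseline is used. If it is the second, a reading 1 mm lower also lowers the dose by 1 U per side.

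**The case against.** **The 48 may be a misprint.** This is a fair point. The same oddly punctuated sentence appears under both methods, and a plan that says the first effect has gone by 8 months has little reason to schedule an average-dose reading after that. If the intended week lies before injection 2, the overlap disappears. The sponsor should therefore be asked before any data are set aside. The order problem would remain.

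**Paired tests are right for a self-controlled study.** Agreed. A reader might infer that the choice of tests creates the confounding, or that a better model would remove it. The design algebra shows otherwise.

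**The washout deals with carry-over.** Eight months and a second baseline make residual effect a lesser concern, and nothing in the documents shows that any persists. But a washout does not remove period effects, and the plan asserts its success without planning a check.

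**Starting low is a cited safety approach.** The background does cite it. A reader might infer that the order must be randomised. That would separate dose from period, though not from unequal carry-over, and about half the participants would get the higher dose first. It is a design trade-off, and the documents do not make it a required change.

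**No bias has been shown.** A reader might infer a definite false-positive rate, or that week 48 will favour the average dose. The documents support neither. They give no sample size, standard deviation or period shift, and they do not say that nominal week-48 values will be compared.

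**Conclusion.** The concern holds in two parts. As written, the average-dose week-48 reading falls about 13.2 weeks after the higher-dose injection (12.6 to 13.7 with 31- or 30-day months, 16 with 4-week months) and cannot measure average-dose duration. This assumes that week 48 is counted from the average-dose injection, which is the plain reading, and that 48 is not a misprint. The effect on a between-dose result is conditional on week-48 values being compared; its size would be whatever the higher dose loses between about 13 and 48 weeks, which the documents do not give.

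Independently of that, the fixed order makes dose and period inseparable by any analysis. The size and direction of a period effect cannot be derived from the documents. What follows is a limit on what may be concluded, not evidence that the result will be wrong.

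**What to change.** 1. **Confirm the visit week.** If 48 is a misprint for a week before injection 2, correct it under both methods. If 48 is right, exclude the first-period week-48 reading from the dose comparison, state that matched duration data stop at week 12, and report the second baseline (about week 35) descriptively as the late average-dose reading. Alternatively, if treatment has not begun, give injection 2 after the week-48 visit.
2. **Compare the baselines.** Report the paired difference between the two pre-injection baselines with a 95% CI, noting that a shortfall mixes residual effect with regression to the mean.
3. **Limit the conclusion** to the higher-dose method given as a second injection after the average dose.

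The correction or exclusion, the baseline comparison and the limited conclusion are changes to text and analysis. They need no new data and can be made even if treatment is complete. The price of exclusion is that no between-dose comparison is left beyond week 12. Delaying injection 2 keeps that comparison but adds about 13 weeks per participant: the last visit moves from 34.8 + 48 = 82.8 weeks to at least 48 + 48 = 96 weeks.

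### For mild gingival smile (3 to <5 mm) the higher-dose period also adds a second injection point, so these participants' paired difference cannot be attributed to dose alone

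*Combined protocol and SAP*

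**What the plan says.** The Study Protocol sets the first (average-dose) injection by severity. Mild: "For mild gingival smile (3-5 mm), a single-site injection of 2 U botulinum toxin type A" per side, in the LLSAN muscle on each side. Moderate and severe: 3 U and 5 U per side. The sentence after these two doses places the injections "at bilateral levator labii superioris alaeque nasi muscles and at the Yonsei point, with half doses administered at each point".

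Eight months later, "all the patients underwent second injection of the higher-dose method". The dose rule is "The injection dose (U) per side was set as the absolute value of the preoperative anterior gingival exposure (mm"), and the same two-point, half-and-half placement is repeated with no exception for mild.

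The title asks whether "Higher-doses of botulinum toxin show better intensity and duration in the treatment of Gummy Smile". The background says that "there are controversies around the optimal dose and injection site of botulinum toxin type A". The aims define the two approaches by units per side (2-5 U against 3-10 U) and say that "healthy participants with gummy smile underwent two treatment methods".

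The Statistical Analysis Plan says that "a paired-samples t-test was used to identify differences", with the Wilcoxon signed-rank and McNemar-Bowker tests for other types of variable. It describes no analysis by severity tier or by injection site.

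**The concern.** Using participants as their own controls removes stable differences between people. It does not remove a second change made within the same person between the two periods. For mild participants the higher-dose period changes two things at once: the total dose and the set of points injected. The background lists site next to dose as unsettled, so by the protocol's own account site may matter.

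What is at stake is attribution. A difference in gingival exposure, duration or side effects among mild participants could come from the larger total dose, the new point, or both. If all participants are analysed together, that mixed contrast enters a result that the title invites the reader to take as an answer about dose.

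**Working it through.** The plan states no sample size, effect size or SD, so there is no design figure to reproduce. The check is a tabulation of the protocol's own dosing rules.

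**Inputs (Study Protocol).** Average dose per side: 2 U at LLSAN only (mild); 3 U (moderate) or 5 U (severe), half at each of two points. Higher dose per side: x U for x mm of exposure, half at each of two points.

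**Assumptions.** (a) Exposure before the second injection equals exposure before the first; the protocol does not say which measurement the word preoperative refers to. (b) Doses are not rounded; no rounding rule is stated.

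**Formulas, per side.**
- Mild: LLSAN 2 → x/2, ratio x/4; Yonsei 0 → x/2; total 2 → x, ratio x/2.
- Moderate: each point 1.5 → x/2, ratio x/3.
- Severe: each point 2.5 → x/2, ratio x/5.

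| Exposure (mm) | LLSAN (U) | Yonsei (U) | Total (U) | LLSAN ratio | Total ratio |
|---|---|---|---|---|---|
| 3.0 (mild) | 2 → 1.5 | 0 → 1.5 | 2 → 3 | 0.75 | 1.50 |
| 4.0 (mild) | 2 → 2.0 | 0 → 2.0 | 2 → 4 | 1.00 | 2.00 |
| 4.5 (mild) | 2 → 2.25 | 0 → 2.25 | 2 → 4.5 | 1.12 | 2.25 |
| 5.0 (as moderate) | 1.5 → 2.5 | 1.5 → 2.5 | 3 → 5 | 1.67 | 1.67 |
| 7.0 (severe) | 2.5 → 3.5 | 2.5 → 3.5 | 5 → 7 | 1.40 | 1.40 |
| 10.0 (severe) | 2.5 → 5.0 | 2.5 → 5.0 | 5 → 10 | 2.00 | 2.00 |

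**Reading the table.** In the moderate and severe tiers both points are used in both periods and scale by the same factor as the total, so site does not change. In the mild tier the total rises for everyone (1.5 to <2.5 times), but the LLSAN amount falls below 4 mm, is unchanged at 4 mm and rises above it. The amount given at the new point, relative to the total added, is (x/2)/(x − 2): 1.5/1 = 1.50 at 3 mm, 2/2 = 1.00 at 4 mm, and 2.5/3 = 0.83 as x approaches 5 mm. The corresponding figure in the other tiers is 0.50.

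**Sensitivity to the assumptions.** With rounding to whole units, the LLSAN fall is confined to 3.0-<3.5 mm (3 U, so 2 → 1.5); 3.5-<4.5 mm is unchanged (4 U, 2 → 2); 4.5-<5 mm rises (5 U, 2 → 2.5). If exposure is re-measured before the second injection, all the ratios change. Under either departure, mild participants still go from one point to two.

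**What cannot be computed.** If a share m of participants is mild and the added point has its own effect S, an all-participant mean difference contains m × S. The documents give neither quantity, so no size, direction or error rate follows.

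**The case against.** The strongest reply is that the trial compares regimens. The aims speak of two methods, and on the protocol's own metric, units per side, the dose rises for every mild participant. This stands: as regimen versus regimen, an all-participant result is legitimate and nothing is wrong with the paired tests. It does not cover the title's question, which is about dose.

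A second reply is that the two-point sentence in the average-dose paragraph covers all tiers, so that mild participants had two points both times. The single-site wording for mild makes this the weaker reading, and the sentence follows directly on the moderate and severe doses. If two points were intended, the text needs correcting.

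Third, the plan never says that the tiers will be combined. That is right: the plan is silent on tiers, and an all-participant analysis is inferred from that silence.

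Fourth, the ≥5 mm group does not isolate dose either, because the average dose always comes first. This also stands. Separating the groups removes the site change, not the period order.

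A reader might go further and infer that the trial is biased, perhaps in favour of the higher dose, or that mild participants below 4 mm were in effect given a lower dose. The documents support neither. The per-point figures describe where toxin is placed, not what it does; nothing in the plan relates dose at a single point to outcome, and total dose rises throughout.

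**Conclusion.** The concern holds in a limited form. For participants with 3 to <5 mm of exposure, the higher-dose period changes total dose and injection site together, so their paired difference cannot be attributed to dose alone. That conclusion rests only on the single-point wording for mild in the first period and the two-point rule for everyone in the second. The per-point amounts (LLSAN 2 U to 1.5-<2.5 U, Yonsei 0 to 1.5-<2.5 U) rest additionally on equal exposure before both injections and on unrounded doses.

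The effect on any overall result is of unknown size and direction. The point is minor: it touches one tier, concerns interpretation, and leaves the regimen comparison intact.

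**What to change.** Report the paired comparison in two groups: participants injected at two points in both periods (≥5 mm), and those injected at one point in the first period (3 to <5 mm). The printed tiers 3-5 and 5-7 mm both include 5 mm, so assign anyone at exactly 5 mm by the points actually injected in the first period. Base statements about dose on the two-point group, and say that the fixed period order remains and that this answer does not extend to mild smiles. Label the mild result dose plus site, and any overall result regimen versus regimen.

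This needs no new data; the cost is precision. With equal SD in both groups, and ignoring the change in the t quantile, the interval width relative to the overall one is 1/√(1 − m) for ≥5 mm and 1/√m for mild. The mild share m is not given, so these values are assumed:

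| Assumed mild share | ≥5 mm | 3 to <5 mm |
|---|---|---|
| 20% | 1.12 | 2.24 |
| 30% | 1.20 | 1.83 |
| 50% | 1.41 | 1.41 |

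Changing the injection points so that they match across periods is not recommended. It would alter the regimens being compared, and the protocol describes the injections in the past tense.
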